Appendix	
1. Summary of investigations, treatment and assessment	15
2. CE certificate	16
3. Reference list	17
4. Participant information sheet 1	
5. Participant information sheet 2	

GLOSSARY OF ABBREVIATIONS

AutoDVT	Automatic deep vein thrombosis software
DVT	Deep vein thrombosis
GP	General Practitioner
IRAS	Integrated research Application system
NHS	National Health System
PI	Principal Investigator
US	Ultrasound
USS	Ultrasound Scan
VTE	Venous Thromboembolism

KEYWORDS

AutoDVT software, non-specialist, DVT, USS, gold standard, benefit

STUDY SUMMARY

TITLE Benefit of Machine learning to diagnose Deep vein Thrombosis compared to gold standard Ultrasound

DESIGN This study aims to compare gold standard DVT diagnostic performed by a specialist sonographer to a scan by a non-specialist with a newly developed AutoDVT detection software device. Currently the process from the DVT symptom begin, to diagnosis and then treatment is all but not straight forward. It implements a laborious journey for the patient from their GP to A & E, then to a specialist sonographer. However, handheld Ultrasound devices have recently become available. The start-up company ThinkSono developed a software, which is hoped to divide between thrombosis and no thrombosis. In this single blinded pilot study, patients which present at St. Mary's DVT Clinic, The Bays will be scanned by the specialist with the gold standard Duplex Sonography and after this by a non-specialist with the machine learning supported device. The accuracy of the device will be compared to the gold standard. This would mean that in future DVT could be diagnosed at point of care by a non-specialist such as a community nurse or nursing home nurse, where patients are multi morbid and limited in their mobility. The technology could reduce emergency department presentations and free up specialist sonographer to focus on other clinical tasks. These improvements could reduce the financial burden of DVT diagnostic services for the NHS.

AIMS "AutoDVT" is a software system designed to assist non-specialist operators, such as nurses, general practitioners (GP) and other allied health professionals in the diagnosis of DVT. The software utilises a "machine learning" algorithm to assist non-specialists in the diagnosis of DVT as described below. Venous thrombosis commonly occurs in the deep leg veins as well as the deep veins of the pelvis, and they are divided clinically into above knee (iliac, femoral, popliteal) and below knee (calf veins) DVT. DVT is well recognised to cause globally significant morbidity and mortality both at the time of diagnosis and post diagnosis. Between 30 – 50% of patients diagnosed with DVT will go on to develop a post-thrombotic syndrome, which has a significant impact on patients' long-term quality of life. Patients with DVT are also at risk of a oft fatal pulmonary embolus (PE), with rates estimated to be 0.4% during the initial anticoagulation period and post-treatment.

According to the Charity Thrombosis UK dies every 37 seconds a person of a venous thromboembolism in developed countries (Thrombosis UK, 2019). However, positive cases only represent 12-25% of the total number of patients who present with suspected DVT. In other words, between 75-88% of suspected DVT cases, when fully investigated, are negative. It is important to note that this does not consider time lost from work, hospitalisation, treatment costs and costs for repeat ultrasound scans. It is notoriously difficult to diagnose a DVT by clinical exam alone. The standard approach to make a diagnosis of proximal DVT currently involves an algorithm combining pre-test probability- Wells Score, D-dimer (blood) testing, and compression ultrasonography (typically a three-point compression examination). There are new handheld ultrasound (US) probes available, meaning only the US probe is required for diagnostic purposes in conjunction with a smartphone or tablet. At present, although the new handheld probes are smaller and are better suited for point of care diagnosis, they still require an experienced radiologist or sonographer to perform the three-point compression exam.

This means that these devices can only be used wherever radiographers/ radiologists are based most often in hospitals. However, due to recent advances in “machine learning”, software is now being developed for these ‘app-based’ probes that can assist non-specialist healthcare professionals to carry out the compression US exam with minimal training. The previous data-collecting study with 53 participants at Oxford University Hospital (OUH) were used to develop a highly sensitive and specific software (AutoDVT) that can be used by non-specialist healthcare professionals.

It is expected that this technology will have similar diagnostic test accuracy to standard compression US. The study outlined in this protocol will test this hypothesis.

OUTCOME MEASURES

1) To compare the accuracy of the AutoDVT software with the scan carried out by a qualified sonographer as part of standard care.

2) To compare the accuracy of the AutoDVT software in perspective of different patient groups.

POPULATION

Patients attending the DVT clinic, The Bay, at St.Mary's NHS Trust with a suspected DVT will be initially screened by the clinical team for potential inclusion into the trial. If the patient is eligible for inclusion in this study, they will be approached to consider taking part in the study. Patients will be given sufficient time to read the participant information sheet, and to consider taking part and ask any questions they may have. If they agree, they will be asked to sign an informed consent form. Once consent has been obtained, the study coordinator, [name] will perform the three-point compression ultrasound scan (USS) with the AutoDVT Software on the participant. At the end of the scan, the AutoDVT software will indicate "exam complete" or "repeat exam". The AutoDVT software will store the results of the scan for analysis and review. Following the AutoDVT scan, patients will continue with the standard DVT diagnostic pathway, including a standard compression ultrasound scan.

ELIGIBILITY

Patients are eligible for this trial if:

[figure not shown]
1. The participant has capacity to consent and consent is obtained
2. The participant is an adult (18 or older in the UK)
3. The participant has symptoms suggestive of a deep venous thrombosis
4. The diagnostic DVT algorithm indicates that an ultrasound is needed

A patient will not be eligible for this study if they fulfil one or more of the following criteria:

1. Patient is under the age of 18.
2. No data of D-dimer result
3. The participant is found to have a distal DVT during the US scan (retrospective exclusion)
4. The participant did not sign the consent form

DURATION 5 months

REFERENCE DIAGRAM

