1. INTRODUCTION

1.1. BACKGROUND

Previous Study:

The AutoDVT software has been piloted at OUH in the UK for image and data collecting to feed the software. Since then, its sensitivity and specificity for DVT detection has been optimised.

(Ethics: 18/SC/0220, IRAS 234007). Hence, this study will compare three-point compression AutoDVT to estimate the sensitivity of the software to detect proximal DVT of the leg compared to the gold standard. Patient groups, which could profit from this new diagnostic tool will be evaluated.

Current Procedure:

Currently the process from the DVT symptom begin, to diagnosis and then treatment is all but not straight forward. It implements a laborious journey for the patient from their GP to A & E, then to a specialist sonographer. However handheld Ultrasound device how recently become available. The start-up company ThinkSono developed a software which is hoped to divide between thrombosis and no thrombosis. In this single blinded pilot study, patients which will present at St Mary's DVT Clinic will be scanned by the specialist with gold standard and after this by a non-specialist with the machine learning supported device. The accuracy of the device will be compared to the gold standard. This would mean that DVT could be diagnosed at point of care by a non-specialist such as a community nurse or nursing home nurse, where patients are multi morbid and limited in their mobility. The technology could reduce emergency department presentations and free up specialist sonographer to focus on other clinical tasks. These improvements could reduce the financial burden of DVT diagnostic services for the NHS.

Risks and benefits for participants of study

Risks:

The risks to participants are minimal with no proven risks from DVT ultrasound. Careful monitoring of adverse events will ensure that any clinical issues are identified promptly. Patients will receive an additional scan of their leg to that of routine clinical care, which may increase the length of time at the clinic. All patients will be fully informed of what the study involves prior to entry.

Benefits:

There is no direct benefit to the participants but there will be a future potential benefit as patients might have access to:

- Rapid access to a diagnostic test
- Local point of care testing, reducing the need for patients to be seen by specialists at hospitals

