1.2. RATIONALE FOR CURRENT STUDY

This study will compare three-point AutoDVT to estimate the sensitivity of the software to detect proximal DVT compared to the gold standard. Patient groups, which could profit from this new diagnostic tool will be evaluated. The aim of the study is to estimate the sensitivity and specificity of the AutoDVT software and AutoDVT with an additional review by a suitably qualified clinician with more than one year of experience diagnosing DVTs (e.g., sonographer or radiologist) compared to two or three-point compression ultrasound exam.

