3. STUDY DESIGN

This is a non-randomised, single-blinded, prospective cohort pilot study.

Participants attending the DVT clinic at St. Mary's NHS Trust with a suspected DVT will be initially screened by the clinical team for potential inclusion into the trial. If the patient is eligible for inclusion, they will be approached to consider taking part in the study. Patients will be given sufficient time to read the participant information sheet, and to consider taking part and ask any questions they may have. If they agree, they will be asked to sign an informed consent form. Once consent has been obtained, [name] will perform the three-point compression ultrasound scan (USS) with the AutoDVT software on the participants. At the end of the scan, the AutoDVT software will indicate "exam complete" or "repeat exam". The AutoDVT software will store the results of the scan for analysis and review. Following the AutoDVT scan, patients will continue with the standard DVT diagnostic pathway, including a standard compression ultrasound scan.

Duration: 5 months

Number and type of subjects: estimation of recruitment of approx. 50 participants

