3.1. STUDY OUTCOME MEASURES

Primary Outcome:

Estimate the sensitivity of the AutoDVT software to detect proximal DVT compared to the gold standard.

Secondary Outcome:

The study will evaluate the accuracy and quality, practicality and user acceptance of the AutoDVT software. (Specificity of AutoDVT, positive and negative predictive values of AutoDVT, imaging failure rates (with reasons), numbers of eligible patients not enrolled (with reasons), duration of AutoDVT scans, number of repeat scans).

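### The Aims say the pilot will test similar accuracy, but it is defined to estimate, and the expected positives could not establish similar sensitivity

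*Protocol*

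**What the plan says.** The Aims in the Study Summary end with an expectation and a promise: the technology "will have similar diagnostic test accuracy to standard compression US. The study outlined in this protocol will test this hypothesis". This is the only explicit hypothesis in the protocol. No margin, threshold or success rule is attached to it.

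The sections that define the study speak of estimation:

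- Section 1.1: "to estimate the sensitivity of the software to detect proximal DVT of the leg compared to the gold standard".
- Section 1.2: "The aim of the study is to estimate the sensitivity and specificity of the AutoDVT software".
- Section 3.1, primary outcome: "Estimate the sensitivity of the AutoDVT software to detect proximal DVT compared to the gold standard". Specificity is secondary: "Specificity of AutoDVT, positive and negative predictive values of AutoDVT".

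Section 2 says that accuracy will be compared with the sonographer's scan, and sets no criterion. Section 3 calls the study a pilot and gives its size as "estimation of recruitment of approx. 50 participants". On how many scans will be positive, the Aims say that "positive cases only represent 12-25% of the total number of patients who present with suspected DVT".

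**The concern.** Testing a hypothesis of similar accuracy and estimating sensitivity are different purposes. The first needs a statement of what counts as similar and enough positive cases to rule out a worse device. The second needs only an honest interval. The Aims claim the first, and the rest of the protocol sets up the second.

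What is at stake is the conclusion. With few positives, a result with no missed DVT is quite likely even for a device that misses a meaningful share of cases. Under the wording of the Aims, such a result could be reported as confirming similar accuracy. The protocol looks ahead to diagnosis by non-specialists at the point of care and to publication, so that reading would matter. Participants' own care is not affected, because Section 6 keeps AutoDVT results from the clinical team.

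**Working it through.** **Inputs.** About 50 participants (Section 3); 12-25% positive among all patients with suspected DVT (Study Summary, Aims). The protocol gives no alpha, power, margin or expected sensitivity. The 50 is a recruitment estimate with no calculation behind it, so there is no figure to reproduce. I use exact (Clopper-Pearson) two-sided 95% limits.

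**Step 1: expected counts, if 12-25% applies to those enrolled.**

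- Positives: 50 × 0.12 = 6 and 50 × 0.25 = 12.5, so about 6 to 13.
- Negatives: 50 × 0.75 = 37.5 and 50 × 0.88 = 44.

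**Step 2: sensitivity with no case missed.** The lower limit is 0.025^(1/n).

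| Positives detected | Exact 95% lower limit |
|---|---|
| 6/6 | 54.1% |
| 12/12 | 73.5% |
| 13/13 | 75.3% |

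With one miss, the intervals are 35.9-99.6% (5/6) and 64.0-99.8% (12/13).

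**Step 3: what could be established.** The best lower limit at these counts is 75.3%. No result with 6 to 13 positives can therefore exclude a sensitivity of 80%. As an illustration only, since the protocol sets no threshold, a lower limit of at least 80% needs 17 positives with none missed, and at least 90% needs 36.

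**Step 4: what could be refuted.** Three misses in 6 gives an upper limit of 88.2%, and five misses in 13 gives 86.1%. Both exclude 90%. The data can count against similar sensitivity.

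**Step 5: how often a flawless result would occur.** The probability is (true sensitivity)^n.

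- True sensitivity 80%: 0.8^6 = 26% and 0.8^13 = 5.5%.
- True sensitivity 90%: 0.9^6 = 53% and 0.9^13 = 25%.

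**Step 6: specificity with no false positives.** The lower limit is 90.5% (37/37) to 92.0% (44/44). The limitation lies with the primary outcome.

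**Step 7: how firm the count is.** By chance alone, the number of positives would lie in about 2-11 at 12% and 7-19 at 25% (central 95% of the binomial distribution). Even 19/19 gives a lower limit of only about 82%. Enrolling only patients for whom the diagnostic algorithm calls for ultrasound (Section 4.2) could raise the count. Excluding distal DVT afterwards (Section 4.3) would lower it. The protocol gives no figure for either effect.

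**The case against.** The strongest reply is that this is one sentence in a summary. Every operative section is modest: pilot, estimate, compare. To test a hypothesis can mean, in ordinary use, to examine an expectation, and a small study can do that (Step 4). Accuracy also includes specificity, which is reasonably supported. Interval methods and precision tables are commonly left to a statistical analysis plan, which is not shown here.

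Much of this stands. It makes the point a wording correction and not a fault of design. What it does not remove is the mismatch: the protocol's only explicit hypothesis is one that its primary outcome is not set up to establish. An analysis plan could not change that stated purpose, nor could it add positives.

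Two stronger readings are tempting, and the documents support neither. A reader might infer that a formal confirmatory test is planned and underpowered; no margin, success rule or power claim appears anywhere, so there is no such test to fault. A reader might also infer that about 50 participants is the wrong size; Section 3 offers it as expected recruitment to a pilot, and it fits estimation.

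**Conclusion.** The point holds as a minor wording correction. The Aims attribute to the study a property that it does not have for its primary outcome. At the expected 6 to 13 positives, a flawless result would still be compatible with a true sensitivity as low as 54% to 75%.

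That range is conditional. It assumes that the positivity quoted for all suspected cases carries over to those enrolled, and the true count could be higher or lower. The mismatch between testing and estimating does not depend on that assumption. Nor, at the expected counts, does the conclusion on sensitivity depend on a particular definition of similar, provided that the definition requires more than about 75%.

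**What to change.** **Study Summary, Aims.** Replace the closing sentence (the second sentence in the first quotation above) with:

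> This pilot will estimate the sensitivity (primary outcome) and specificity (secondary outcome) of AutoDVT relative to the standard scan, with exact 95% confidence intervals; it is not designed to establish similar accuracy.

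**Section 3.** Beside the recruitment figure add:

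> If 12-25% are positive, about 6 to 13 positives are expected; with none missed the exact 95% lower limit for sensitivity would be 54% to 75%; selection by the diagnostic algorithm may raise, and exclusion of distal DVT may lower, the number of positives.

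The added text should keep to the protocol's own 12-25% and give no limits for other prevalences, because the protocol supplies no figures for them. It should also leave out the variant described in Section 1.2, "AutoDVT with an additional review by a suitably qualified clinician with more than one year of experience diagnosing DVTs", which appears in neither the objectives nor the outcomes. The first objective in Section 2 can stay as it is.

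The cost is two short edits and a more modest stated aim, with no extra patients, procedures or data.

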1. INTRODUCTION

1.1. BACKGROUND

Previous Study:

The AutoDVT software has been piloted at OUH in the UK for image and data collecting to feed the software. Since then, its sensitivity and specificity for DVT detection has been optimised.

(Ethics: 18/SC/0220, IRAS 234007). Hence, this study will compare three-point compression AutoDVT to estimate the sensitivity of the software to detect proximal DVT of the leg compared to the gold standard. Patient groups, which could profit from this new diagnostic tool will be evaluated.

Current Procedure:

Currently the process from the DVT symptom begin, to diagnosis and then treatment is all but not straight forward. It implements a laborious journey for the patient from their GP to A & E, then to a specialist sonographer. However handheld Ultrasound device how recently become available. The start-up company ThinkSono developed a software which is hoped to divide between thrombosis and no thrombosis. In this single blinded pilot study, patients which will present at St Mary's DVT Clinic will be scanned by the specialist with gold standard and after this by a non-specialist with the machine learning supported device. The accuracy of the device will be compared to the gold standard. This would mean that DVT could be diagnosed at point of care by a non-specialist such as a community nurse or nursing home nurse, where patients are multi morbid and limited in their mobility. The technology could reduce emergency department presentations and free up specialist sonographer to focus on other clinical tasks. These improvements could reduce the financial burden of DVT diagnostic services for the NHS.

Risks and benefits for participants of study

Risks:

The risks to participants are minimal with no proven risks from DVT ultrasound. Careful monitoring of adverse events will ensure that any clinical issues are identified promptly. Patients will receive an additional scan of their leg to that of routine clinical care, which may increase the length of time at the clinic. All patients will be fully informed of what the study involves prior to entry.

Benefits:

There is no direct benefit to the participants but there will be a future potential benefit as patients might have access to:

- Rapid access to a diagnostic test
- Local point of care testing, reducing the need for patients to be seen by specialists at hospitals
- Reduced need for prophylactic anticoagulation whilst waiting for a scan, thereby reducing the potential risk to patients of bleeding whilst taking an anticoagulant medication
- Reduced cost for diagnosis to NHS due to no longer requiring radiographer led services and high technology US devices and reduces the use of anticoagulation
- Higher patient satisfaction with their diagnostic clinical pathway

1.2. RATIONALE FOR CURRENT STUDY

This study will compare three-point AutoDVT to estimate the sensitivity of the software to detect proximal DVT compared to the gold standard. Patient groups, which could profit from this new diagnostic tool will be evaluated. The aim of the study is to estimate the sensitivity and specificity of the AutoDVT software and AutoDVT with an additional review by a suitably qualified clinician with more than one year of experience diagnosing DVTs (e.g., sonographer or radiologist) compared to two or three-point compression ultrasound exam.

2. STUDY OBJECTIVES

The primary objectives of this pilot study are:

- 1) To compare the accuracy of the AutoDVT software with the scan carried out by a qualified sonographer as part of standard care.
- 2) To compare the accuracy of the AutoDVT software in perspective of different patient groups.

3. STUDY DESIGN

This is a non-randomised, single-blinded, prospective cohort pilot study.

Participants attending the DVT clinic at St. Mary's NHS Trust with a suspected DVT will be initially screened by the clinical team for potential inclusion into the trial. If the patient is eligible for inclusion, they will be approached to consider taking part in the study. Patients will be given sufficient time to read the participant information sheet, and to consider taking part and ask any questions they may have. If they agree, they will be asked to sign an informed consent form. Once consent has been obtained, [name] will perform the three-point compression ultrasound scan (USS) with the AutoDVT software on the participants. At the end of the scan, the AutoDVT software will indicate "exam complete" or "repeat exam". The AutoDVT software will store the results of the scan for analysis and review. Following the AutoDVT scan, patients will continue with the standard DVT diagnostic pathway, including a standard compression ultrasound scan.

Duration: 5 months

Number and type of subjects: estimation of recruitment of approx. 50 participants

3.1. STUDY OUTCOME MEASURES

Primary Outcome:

Estimate the sensitivity of the AutoDVT software to detect proximal DVT compared to the gold standard.

Secondary Outcome:

The study will evaluate the accuracy and quality, practicality and user acceptance of the AutoDVT software. (Specificity of AutoDVT, positive and negative predictive values of AutoDVT, imaging failure rates (with reasons), numbers of eligible patients not enrolled (with reasons), duration of AutoDVT scans, number of repeat scans).

